10.1.1. Adverse Events of Special Interest

An adverse event of special interest (AESI; serious or non-serious) is one of scientific and medical interest specific to the sponsor's product or program, for which ongoing monitoring and rapid communication by the PI to the sponsor can be appropriate. Such an event might warrant further investigation in order to characterize and understand it. AESI will be identified using both CRF flag and SMQ search criteria, and needs clinical adjudication.

List of below is AESI for this study:

• Systemic or severe hypersensitivity reactions

Detailed filter of AESI criteria is specified in Section 14.4.

10.2. Laboratory Parameters

The following laboratory tests will be collected and summarized according to the Schedule Events in Section 14.2:

Blood Chemistry

Sodium Total protein, serum Aspartate aminotransferase (AST)
Potassium Creatinine Alanine aminotransferase (ALT)

Chloride Blood urea nitrogen (BUN) Alkaline phosphatase

Carbon dioxide Total bilirubin Albumin

Calcium Glucose

Albumin

Blood chemistry samples should be collected prior to the administration of study drug and prior to EEU challenges, when applicable.

Hematology

Hemoglobin Differential:

Hematocrit Neutrophils
Red blood cells (RBCs) Lymphocytes
White blood cells (WBCs) Monocytes
Red cell indices Basophils
Platelet count Eosinophils

Urinalysis

Color Glucose RBC

Clarity Blood WBC

pH Bilirubin Bacteria

Specific gravity Leukocytes esterase Epithelial cells

Ketones Nitrite Yeast

Protein

Other Laboratory Tests

Participants will be tested for FSH levels (if postmenopausal status is in question) and will undergo serum and urine pregnancy testing (women of childbearing potential only); pregnancy testing is not required of women confirmed to be menopausal. Samples will be collected for quantitative assessment of allergen specific IgE.

Clinical laboratory analytes will be converted to standard international (SI) units and grouped by function in summary tables. Below statistic summaries will be provided:

- Descriptive statistics of clinical laboratory values and change from baseline in clinical laboratory values to all scheduled assessment times by visit and by treatment group
- Number (n) and percentage (%) of participants with a treatment-emergent potentially clinically significant value (PCSV) at any post-randomization time point

Patient laboratory parameter measurements will be evaluated by PCSV criteria, specifically identifying participants with at least one post-baseline measurement that meets the PCSV criteria (Section 14.3). Participants meeting the PCSV criteria will be summarized by patient count (and percent) for a post-baseline PCSV measurement by treatment group, regardless of baseline PCSV status. When the PCSV definition involves a change from baseline value, participants must have a baseline value to be included in the summaries. All measurements collected during the study including, values from unscheduled visits, will be used in the PCSV analyses.

10.3. Vital Signs

The following vital signs parameters will be recorded pre-dose and 2 hours post dose, and summarized according to the Schedule Events in Section Section 14.2:

- Temperature
- Systolic/diastolic blood pressure
- Heart rate
- Respiration rate

Summaries of vital sign variables will include:

- Descriptive statistics of vital sign variable and change from baseline by visit by treatment group
- The number (n) and percentage (%) of subjects with treatment-emergent PCSV

10.4. Other Safety Data

A standard 12-lead ECG will be performed at the screening visit/baseline only. Heart rate will be recorded from the ventricular rate and the PR, QRS, and QT (identify QTcB or QTcF) will be recorded. The ECG strips or reports will be retained with the source documentation.

10.5. Immunogenicity Data

Samples for ADA measurement will be collected at visits listed according to Schedule Events in Section 14.2. The samples are to be collected prior to the administration of study drug. In the event of suspected SAEs, such as anaphylaxis or systemic hypersensitivity, additional samples for the analysis of ADA may be collected as close to the event as practically possible.

10.5.1. Immunogenicity Variables

The immunogenicity variables include ADA status, titer at nominal sampling time/visit. Serum samples for ADA will be collected at the clinic visits specified in Section 14.2. For each study drug, samples positive in the ADA assay will be further characterized for ADA titers.

10.5.2. Analysis of Immunogenicity Data

The immunogenicity variables described in Section 10.5.1 will be summarized using descriptive statistics. Immunogenicity will be characterized per drug molecule by ADA status, ADA category and maximum titer observed in participants in the ADA analysis sets. For samples confirmed as drug specific ADA positive, but found negative at the lowest titer dilution, the lowest dilution in the titer assay is imputed.

The ADA status of each participant may be classified as one of the following:

- Positive
- Pre-existing If the baseline sample is positive and all post baseline ADA titers are reported as less than 9-fold the baseline titer value
- Negative If all samples are found to be negative in the ADA assay.

The ADA category of each positive participants is classified as:

- Treatment-boosted A positive result at baseline in the ADA assay with at least one post baseline titer result ≥ 9-fold the baseline titer value
- Treatment-emergent A negative result or missing result at baseline with at least one positive post baseline result in the ADA assay. Participants that are treatment-emergent will be further categorized as follows:

Treatment-emergent is further sub-categorized as:

- Persistent A positive result in the ADA assay detected in at least 2 consecutive post baseline samples separated by at least a 16-week post baseline period [based on nominal sampling time], with no ADA-negative results in-between, regardless of any missing samples
- Transient Not persistent or indeterminate, regardless of any missing samples
- Indeterminate A positive result in the ADA assay at the last collection time point only, regardless of any missing samples

The maximum titer category of each participant is classified as:

- Low (titer < 1,000)
- Moderate $(1,000 \le \text{titer} \le 10,000)$
- High (titer > 10,000)

The following will be summarized by treatment group and ADA titer level:

- Number (n) and percent (%) of ADA-negative participants
- Number (n) and percent (%) of pre-existing participants

- Number (n) and percent (%) of treatment-emergent ADA positive participants
 - Number (n) and percent (%) of persistent treatment-emergent ADA positive participants
 - Number (n) and percent (%) of indeterminate treatment-emergent ADA positive participants
 - Number (n) and percent (%) of transient treatment-emergent ADA positive participants
- Number (n) and percent (%) of treatment-boosted ADA positive participants

Listing of all ADA titer levels will be provided for participants with pre-existing, treatment-emergent and treatment-boosted ADA response.

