5.2. Treatment Period Dispositions

A patient is considered to have completed the study treatment period if they make it to the Endorf-Study Visit (visit 15/day 253). The disposition of all randomized participants during the study treatment period will be displayed by treatment group.

The following summaries will be provided for each treatment group and total (unless otherwise specified):

- Study drug administration
- The total number of participants in each analysis set
- The number of participants who complete the study treatment period
- Duration of study treatment period
- The number of participants completing each visit
- The number of participants who withdraw from the study treatment period. This number will be further broken out by reason for early withdrawal and whether the early termination/ withdrawal was prior to or after the start of the local BPS.

DEMOGRAPHICS AND BASELINE CHARACTERISTICS 6.

6.1. **Demographics**

The following demographic variables will be summarized by treatment group and overall:

- Age at screening (years) as a continuous variable
- Age categories (years, 18 to <50, >=50)
- Sex (Male, Female)
- Race (American Indian or Alaskan Native, Asian, Black or African American, Native Hawaiian or Other Pacific Islander, White, Not Reported)

Date: May 31, 2023

- Ethnicity (Hispanic or Latino, Not Hispanic or Latino, Not Reported)
- Weight (kg)
- Height (cm)
- Body mass index (BMI) (kg/m2)
- EEU location (Cliantha, Kingston)
- Site location (Cliantha, Kingston, CSAC)

6.2. **Baseline Disease Characteristics**

The following disease characteristics will be summarized by treatment group and overall:

- Birch EEU Mean TNSS (2 to 6 hours), Mean TOSS (2 to 6 hours), Mean TSS (2 to 6 hours) at Visit 2
- Oak EEU Mean TNSS (2 to 6 hours), Mean TOSS (2 to 6 hours), Mean TSS (2 to 6 hours) at Visit 3 [only for oak-allergic participants, i.e., those who developed a TNSS of at least 6 out of 12 at 2 or more timepoints during the screening oak EEU at visit 3]
- Screening and randomization FEV1 (L and percent predicted)
- Baseline history for allergic disease, including duration of disease [e.g., allergic rhinitis, allergic conjunctivitis, asthma and pollen food allergy, and prior SIT] (as recorded in CRF)
- SPT mean wheal diameter for birch allergens, birch-related allergens, and unrelated allergens (mm)
- Serum total IgE (kU/L)
- Serum allergen-specific IgE for birch allergens, birch-related allergens, and unrelated allergens (kU/L)

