Visit (V) Number	V1 ¹	V2 ⁵	V3 ⁶	V4	V5	V6	V7 ⁶	V8 ⁴⁰	V9 ⁴¹	V10 ^{13,41}	V11 ^{12,13}	V12 ¹³	V13 ¹³	V14 ¹³	V15 ¹³	
Appx. Week (wk)		l			wk1	wk4	wk5	wk8	wk12	~wk18	~wk22		~wk27	~wk32	~wk36	
Visit Day (d)	-d70	0 to -d1		d1	d8	d29	d36	d57	d85	d127	d155	d156	d190	d225	d253	
Visit Window (days)					±3d	±7d	-7d to +14d	±7d	-28d to +14d	±7d	±7d	+1d	±7d	±7d	±7d	
Exploratory research serum and plasma ³²		X		X		X		X	X		X		X	X	X	
Treatment:																
Randomization				X^{10}												
Administer study drug ¹⁶				X							X ^{11,14}					
Dispense rescue medications ²⁷		X	X			X	X	X	X	X	X		X	X		
Efficacy:																
EEU visits: TNSS, TOSS ^{7,8,9}		X ⁵	X			X^7	X^7	X^7	X^7				X^8	X^8		
e-Diary: TNSS, TOSS, and DMS ²⁴			X^{25}									X	7 26			
RQLQ(S) ²⁸		X]	X				
PFASQ ²⁹		X							X							
Outdoor time questionnaire ³⁰		X								X						

				PA	RT A							PAI	RT B			
	SCRI	EENINC	ĵ	RAND		Οι	ut-of-Sea	ason					FOLLOW- UP			
Study Procedure	Screening	Birch EEU	Oak EEU	Rand/ Dosing	Tel	Birch EEU	Oak EEU	Birch EEU	Birch EEU	In- Clinic	Dosing	Tel ¹⁵	Birch EEU	Birch EEU	EOS/ ET	Unsc. Visit ³⁸
Visit (V) Number	$V1^1$	V2 ⁵	V3 ⁶	V4	V5	V6	V7 ⁶	V8 ⁴⁰	V9 ⁴¹	V10 ^{13,41}	V11 ^{12,13}	V12 ¹³	V13 ¹³	V14 ¹³	V15 ¹³	
Appx. Week (wk)		l			wk1	wk4	wk5	wk8	wk12	~wk18	~wk22		~wk27	~wk32	~wk36	
Visit Day (d)	-d70) to -d1		d1	d8	d29	d36	d57	d85	d127	d155	d156	d190	d225	d253	
Visit Window (days)					±3d	±7d	-7d to +14d	±7d	-28d to +14d	±7d	±7d	+1d	±7d	±7d	±7d	
Safety:																
Vital signs ¹⁸	X	X	X	X		X	X	X	X	X	X		X	X	X	X
Physical examination ¹⁷	X	X	X	X		X	X	X	X	X	X		X	X	X	X
Adverse events	X	X	X	X	X	X	X	X	X	X	X	X	X	X	X	X
Concomitant medications	X	X	X	X	X	X	X	X	X	X	X	X	X	X	X	X
Spirometry/PEF ²³	X ^{23*}	X	X	X ^{23*}		X	X	X	X		X		X	X		X
Laboratory Testing ²	0:															
Hematology ³²	X			X		X		X	X	X			X	X		X
Blood chemistry ³²	X			X		X		X	X	X			X	X		X
Pregnancy test (urine) (WOCBP) ²¹		X	X	X		X	X	X	X		X		X	X	X	X
Pregnancy test (serum) (WOCBP) ²¹	X									X						X
Pharmacokinetics an	nd Immuno	genicity	Samp	ling:												
Drug concentration sample ³⁶				X ³⁶		X		X	X	X	X ³⁶		X	X	X	X
ADA sample ³⁶				X ³⁶					X		X ³⁶				X	X

		PART A										PAI	RT B			
	SCRI	EENINC	j	RAND		Out-of-Season								FOLLOW- UP		
Study Procedure	Screening	Birch EEU	Oak EEU	Rand/ Dosing	Tel	Birch EEU	Oak EEU	Birch EEU	Birch EEU	In- Clinic	Dosing	Tel ¹⁵	Birch EEU	Birch EEU	EOS/ ET	Unsc. Visit ³⁸

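### The 16-week rule for persistent ADA does not fit the ADA sampling days, so some participants still positive at their last sample are counted as transient

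*SAP*

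**What the plan says.** SAP 10.5.2 divides treatment-emergent ADA into three sub-categories.

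- *Persistent*: at least two consecutive positive post-baseline samples, "separated by at least a 16-week post baseline period", with no negative between them. The time scale is "based on nominal sampling time".
- *Indeterminate*: "A positive result in the ADA assay at the last collection time point only".
- *Transient*: the remainder, "Not persistent or indeterminate, regardless of any missing samples".

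The same section commits to reporting the number and percentage in each sub-category by treatment group.

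On sampling, SAP 10.5.1 says "Serum samples for ADA will be collected at the clinic visits specified in Section 14.2". The ADA row of that schedule marks visits 4 (baseline), 9, 11 and 15, plus unscheduled visits. From visit 9 onward the visit-day row reads "d85 d127 d155 d156 d190 d225 d253". SAP 2.1 confirms visit 9 as day 85, and SAP 5.2 confirms the end of study as "visit 15/day 253". SAP 10.5 adds: "The samples are to be collected prior to the administration of study drug". The visit 11 sample therefore precedes dose #2.

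**The concern.** A persistence rule has to be one that the sampling schedule can test. Here the required separation is longer than the gap between any two neighbouring scheduled samples. Transient is also a pure remainder class, which never requires ADA to disappear. Together these place some participants whose last available sample is positive in a category that most readers take to mean a response that went away.

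Immunogenicity after single and repeat dosing is a stated secondary objective (Protocol 2.2, SAP 1.1.2), and Protocol 3.3 names it as an important potential risk. The counts go straight into a planned table. If few participants develop ADA, one label can change how that table reads.

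**Working it through.** **Inputs** (SAP 14.2, same in Protocol Table 1): visit 9 = day 85, visit 11 = day 155 (pre-dose), visit 15 = day 253. The threshold in SAP 10.5.2 is 16 weeks = 16 × 7 = 112 days, on nominal time.

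**Reproducing the schedule's week labels**, with week = (day − 1)/7:

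- (85 − 1)/7 = 12
- (155 − 1)/7 = 22
- (253 − 1)/7 = 36

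These match the printed weeks 12, 22 and 36, so the nominal days have been read correctly.

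**Gaps between post-baseline samples**

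| Pair | Days | Weeks | At least 16 weeks? |
|---|---|---|---|
| Visit 9 to 11 | 155 − 85 = 70 | 10 | No |
| Visit 11 to 15 | 253 − 155 = 98 | 14 | No |
| Visit 9 to 15 | 253 − 85 = 168 | 24 | Yes |

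**Applying the rule.** The text does not say how the 16 weeks is measured. Reading A runs from the first to the last positive in an unbroken run. Reading B applies between two adjacent available samples. Results are in the order day 85, 155, 253 (+ positive, − negative, m missing).

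| Pattern | Reading A | Reading B | Last available sample |
|---|---|---|---|
| + + + | persistent | transient | positive |
| + m + | persistent | persistent | positive |
| − + + | transient | transient | positive |
| m + + | transient | transient | positive |
| + + m | transient | transient | positive |
| + − + | transient | transient | positive |
| + + − | transient | transient | negative |
| − − + | indeterminate | indeterminate | positive |

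For − + + the steps are: 14 < 16 weeks, so not persistent; two positives, so not positive at the last time point only; therefore transient.

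**Counting patterns, not participants.** Three results at three visits give 27 patterns, of which 2 × 2 × 2 = 8 contain no positive, leaving 19. Taking the last time point as the last available sample, Reading A gives 2 persistent, 7 indeterminate and 10 transient. Of the 10 transient patterns, four end on a positive sample: − + +, m + +, + + m and + − +. Reading B moves + + + across, giving five of 11.

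**Visit windows.** With the ±7-day windows at visits 11 and 15, the longest actual gap is (253 + 7) − (155 − 7) = 112 days, exactly 16 weeks. The schedule footnotes also let Part B visits move with the season. Neither helps, because the rule uses nominal time. A participant sampled 16 or more actual weeks apart would still be assigned the nominal 14.

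**Alternative threshold.** A threshold of 14 weeks or less would make − + + and m + + persistent. Any threshold above 14 weeks leaves them transient.

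**The case against.** The strongest case against is that little depends on this split. The secondary endpoint is ADA incidence and titer over time, and the immunogenicity analysis in Protocol 10.4.7 has no persistent/transient split. The associations with safety and efficacy in SAP 10.5.3.2 use treatment-emergent, treatment-boosted and titer categories. SAP 10.5.2 also lists all titers for every such participant, so continuing positivity stays visible. Protocol 3.2.2 reports no treatment-emergent or treatment-boosted ADA in either earlier study. All of this stands and limits the size of the point. Two qualifications apply: those studies gave single doses of the three-antibody product, and a listing does not correct a summary count.

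A second objection is that the SAP never says transient means resolved, and that a response seen over 14 weeks has not been shown to last 16. That is literally true. It supports a separate class for such responses, but not pooling them with responses that were followed by a negative sample.

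Several stronger readings are tempting, and the documents do not support them:

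- *Anyone positive at the last two samples is transient.* Not if day 85 is also positive: that run spans 24 weeks and is persistent under Reading A.
- *The rule cannot be met.* It can, when days 85 and 253 are both positive and day 155 is missing, or positive under Reading A.
- *Every run of two positives is misclassified.* Days 85 and 155 positive with day 253 negative is reasonably called transient.
- *ADA induced by dose #2 is understated.* The day 155 sample precedes dose #2. ADA first arising after dose #2 has one scheduled sample, day 253, and can only be indeterminate under any version of the rule.

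**Conclusion.** The point holds in a limited form. On scheduled samples, ADA first detected at day 155 can never be called persistent. If it is still present at day 253, it is reported as transient. The same happens to a response positive at days 85 and 155 with no later sample. Under Reading B, it also happens to a participant positive at all three visits. The stated rule therefore produces a misleading count, so this is more than a missing detail.

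The effect is confined to one descriptive sub-classification. Treatment-emergent incidence, treatment-boosted counts, titers and efficacy inference do not change, and few participants are likely to be involved. The conclusion rests on the nominal visit days and on scheduled samples. An unscheduled sample adds a time point but does not lengthen the 14 weeks between visits 11 and 15.

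**What to change.** Rewrite the sub-categories in SAP 10.5.2 so that the schedule can support them:

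1. State that the interval runs from the first to the last positive in an unbroken run. Keep the existing allowance for missing samples.
2. Restrict *transient* to participants whose last available post-baseline sample is negative.
3. Class as *persistent*, or as a separate class *ongoing at last sample*, participants positive in two or more consecutive scheduled samples up to and including their last available one. Require a minimum nominal interval of 10 weeks, which is the shortest scheduled gap. A minimum is needed because unscheduled samples are allowed, and two positives days apart should not qualify.
4. Keep *indeterminate* for participants positive only at the last available sample.
5. Assign explicitly the patterns that remain: positive-negative-positive, and a run that reaches the last sample but spans less than 10 weeks.

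Lowering the threshold to 10 weeks alone is not enough. It would make positive-positive-negative persistent despite the later negative sample, so the condition in item 3 that the run reach the last available sample must go with it.

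The cost is one SAP definition and the matching table programming, with no new samples, visits or assays. It should be settled before ADA results are reviewed by treatment group.

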10.5.3. Association of Immunogenicity with Exposure, Safety and Efficacy

10.5.3.1. Immunogenicity and Exposure

Potential association between immunogenicity and systemic exposure to REGN5713, REGN5714, and REGN5715 will be explored by treatment groups. Plots of individual REGN5713, REGN5714, and REGN5715 concentration time profiles by ADA status or titer may be provided to examine the potential impact of ADA on systemic exposure.

10.5.3.2. Immunogenicity and Safety and Efficacy

Potential association between immunogenicity variables and safety may be explored with a primary focus on the following safety events during the TEAE period:

- Injection site reaction (serious or severe)
- Hypersensitivity (SMQ: Hypersensitivity [Narrow])
- Anaphylaxis (SMQ: Anaphylactic Reaction [Narrow])

Potential association between immunogenicity variables and efficacy endpoints may be explored (e.g., scatter plot or spaghetti plot).

The safety and efficacy analyses mentioned above will be conducted using the following categories:

- ADA Positive
 - Treatment-emergent
 - Treatment-boosted
- Maximum post-baseline titer category in ADA positive participants

10.6. Pharmacokinetic Data

10.6.1. Pharmacokinetic Variables

Concentrations in serum of total (free + antigen bound) REGN5713, REGN5714, and/or REGN5715 will be measured at time points specified in the study schedule of events in Section 14.2 . Pharmacokinetic variables consist of concentrations of individual antibodies (REGN5713, REGN5714, and/or REGN5715) as well as total drug (REGN5713+REGN5714+REGN5715 or REGN5713+REGN5715) in serum, and time (both nominal and actual time).

10.6.2. Analysis of Pharmacokinetic Data

Descriptive statistics of total REGN5713, total REGN5714, total REGN5715, and/or total drug (REGN5713+REGN5714+REGN5715 or REGN5713+REGN5715) concentrations in serum at each sampling timepoint will be provided. Plots of mean concentration versus nominal time may be presented. Select PK parameters may be calculated.

Exposure Response analysis of biomarkers, efficacy, and safety endpoints may be conducted as necessary and presented in separate reports.

10.7. Biomarker Data

Exploratory biomarker data may be described in a separate exploratory analysis plan. Analyses may include (but are not limited to) evaluating relationships between biomarkers and clinical responses. Exploratory biomarker variables may include (but are not limited to) serum allergenspecific IgE levels (birch, Bet v 1, Bet v 2, and other common allergens) and basophil activation. Relevant biomarker data analyses may be included in the CSR and/or a separate biomarker report.

11. **DATA CONVENTIONS**

11.1. **Definition of Baseline for Efficacy/Safety Variables**

Unless otherwise specified, the Baseline assessment for all measurements will be the latest available valid measurement taken prior to the administration of investigational product. The following rules specify the determination of baseline by both date/time information:

• The date and time of first injection will be used to determine the baseline for the AE, lab, PK and ADA data.

Date: May 31, 2023

• Only the date of first injection will be used to determine the baseline for other data except the AE, lab, PK and ADA data.

For the efficacy endpoints, the baseline is defined as following:

- For all symptom scores (TNSS or TOSS) collected in EEU chambers, the baseline is defined as the mean of the corresponding measurements (2 to 6 hours) during the allergen EEU challenge in screening period. The baseline visit for Birch is Visit 2, and the baseline visit for Oak is Visit 3.
- For daily e-diary scores (daily TNSS, daily TOSS, DMS, daily TSS, daily CSMS, RQLQ(S), PFASQ, and outdoor questionnaire), there are two baselines defined, pretreatment baseline and pre-season baseline.
 - The pre-treatment baseline is defined as the average of the daily score during the screening period before the first dose. All days with scores during the screening period will be used to calculate the average, except for the day of and one day following EEU challenge.
 - The pre-season baseline is defined as the average of the daily score start from the Visit 10 to the day before the local BPS, except for the day of and one day following EEU challenge.

The number of non-missing daily records must be at least 3 after excluding the records happening on the same day and the next day of the EEU visit for pre-treatment and preseason baseline (both pre-treatment baseline) calculation. If the baseline value is smaller than 1, the baseline will be set to 1.

For the rescreened participants, only data from the enrolled subject ID will be used.

11.2. **Data Convention**

For the laboratory safety variables and biomarker data, if the data are below the lower limit of quantification (LLOQ)/limit of linearity, half the lower limit value (i.e., LLOQ/2) will be used for quantitative analyses. For data above the upper limit of quantification (ULOO)/ limit of linearity, the upper limit value (i.e., ULOQ) will be used for quantitative analyses.

Note that for total IgE, Birch sIgE, and Bet v 1 sIgE, samples whose data are above the ULOQ will be re-analyzed at 1:10 dilution and IgE/sIgE levels will be derived from the results of the dilution assay (i.e, calculated using a factor of 10). For mis-stratification, data from oak allergy status (yes or no) determined based on oak EEU challenge, grass sensitization status (grass

sensitized: grass SPT \geq 3 mm or sIgE \geq 0.35; not grass sensitized: grass SPT \leq 3 mm and sIgE \leq 0.35) and EEU site as collected from CRF will be used for analysis rather than as randomized.

